7.4.1.1 Duration of Study Therapy

The number of cycles of treatment received by subjects will be summarized (using n, mean, STD, median, min, max, q1 and q3) by treatment group.

The duration of each treatment (elotuzumab, dexamethasone [oral, IV, and oral and IV combined] and lenalidomide), in months, will be calculated as:

$$(date\ of\ last\ dose\ of\ the\ drug - date\ of\ first\ dose\ of\ the\ drug + 1) / 30.4375$$

Duration of each of the study treatments will be summarized by treatment group.

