7.6.1 Adverse Events

AEs will be categorized using the most recent version of the MedDRA, by system organ class (SOC) and preferred term. The severity of AEs will be graded using the NCI CTCAE (v 3.0).

On-study AEs are defined as non-serious and serious AEs with an onset date on or after the first dose until 60 days after the last dose. See [Section 8.4](#), Imputing AE Onset Dates, for a discussion of imputation rules for incomplete or missing AE onset dates. If the relationship to study drug is missing, then the AE will be assumed to be related to study drug.

Unless specified otherwise, AEs will be counted only once within each SOC and preferred term, according to their worst CTC grade.

Tables will be sorted by SOC and preferred term, with SOCs ordered by decreasing frequency overall and then alphabetically. Preferred terms will be sorted within SOCs by descending frequency overall and then alphabetically. The sorting will be done based on the total column when arms are presented side-by-side.

Frequency tables of the worst grade of on-study AE will be presented. One summary table will present AEs broken out by individual grade, 1, 2, 3, 4 or 5 along with an Any Grade category. Another one will present AEs by grouped grades as follows “Any, Grade 3-4 and Grade 5.” These summaries will be repeated for on-study drug-related AEs.

A by-subject listing all AEs will be presented.

In addition the following will be presented by treatment arm:

- Frequency of AE before and after cycle 18 for subjects on the Elotuzumab arm
- Exposure-adjusted AE incidence rates (including multiple occurrences of unique events) will be calculated for each SOC and preferred term.

Exposure-adjusted incidence rate per 100 person-years will be used and will be calculated as:

$$100 \times \left(\frac{\text{Total number of unique AEs}}{\frac{\text{subject date of last dose of study drug} - \text{subject date of first dose of study drug} + 60 + 1}{365.25}} \right)$$

and will be displayed along with a count of events. For these additional tables, AEs can be counted multiple times within each SOC and preferred term.

A by-subject listing of unique AEs will be provided.

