7.6.2 Serious Adverse Events and Adverse Event Leading to Discontinuation

Summaries of worst grade of on-study SAE, both by individual grade (1, 2, 3, 4, or 5, along with an Any Grade category) and by grade grouped as “Any, Grade 3-4 and Grade 5” will also be presented. These summaries will be repeated for:

- On-study drug-related SAEs
- On-study AEs leading to discontinuation.
- Drug related AEs leading to discontinuation

By-subject listings of SAEs and AEs leading to study drug discontinuation will be produced.

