7.6.4 Adverse Events of Special Interest

Infusion reaction is a known elotuzumab toxicity. It will be based on investigator assessment and will be defined as any non-serious or serious adverse event judged by the investigator to be infusion related and which also occurs on the day of or the day after the elotuzumab infusion. These summaries will be presented:

- Frequency tables of the worst grade of on-study investigator infusion reaction (any grade and grade 1 through 5) by treatment group. The same summary will be presented with grades grouped as Any, Grade 3-4 and Grade 5.
- Frequency of infusion reaction by infusion rate.
- Frequency of infusion reaction by cycle.

By-subject listings of infusion reactions will be produced.

Multiple myeloma is associated with immune dysfunction and the natural course of the disease includes increased infection risk. In addition, elotuzumab may inhibit some cellular components of the immune system. Therefore, a thorough characterization of infections will be presented. Infections will be based on the SOC ‘infections and infestations’ and opportunistic infections will be based on clinically pre-defined PT terms:

- Time to onset and duration of first infection
- Frequency of infections including opportunistic infections by treatment group.
- Absolute lymphocyte count at time of first infection
- Kinetics of lymphocyte reduction

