7.6.5 Second Primary Malignancies

A summary table and a by-subject listing of second primary malignancies (SPM) will be provided. In addition, exposure-adjusted SPM incidence rates (including multiple occurrences of unique events) will be presented by treatment group and will be calculated as follows:

$$100 \times \left(\frac{\text{Total number of unique SPM events}}{\frac{\text{subject death date or last known alive date} - \text{subject date of first dose of study drug} + 1}{365.25}} \right)$$

Information on SPM will be obtained from the on-treatment eCRF page for secondary malignancies and the “Survival Status” eCRF page.

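### Grade 3-4 AEs, SAEs and drug-related SAEs get no exposure-adjusted rate, so their arm comparison mixes event rate with time on treatment

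*SAP*

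**What the plan says.** SAP 7.6.1 (Adverse Events) counts on-study AEs "with an onset date on or after the first dose until 60 days after the last dose". It plans one person-time measure: "Exposure-adjusted AE incidence rates (including multiple occurrences of unique events) will be calculated for each SOC and preferred term". The rate is per 100 person-years, covers all AEs, and is split by neither grade, seriousness nor relationship. It is given by arm, "and will be displayed along with a count of events".

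The severe and serious categories are shown per subject:

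- **Grade 3-4 AEs (7.6.1):** worst-grade frequency tables. "Another one will present AEs by grouped grades as follows" any grade, Grade 3-4 and Grade 5.
- **SAEs (7.6.2):** "Summaries of worst grade of on-study SAE, both by individual grade" and by grouped grade, repeated for drug-related SAEs.
- **Infections (7.6.4):** "Frequency of infections including opportunistic infections by treatment group", with time to onset and duration of the first infection.

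The only other person-time rate is in 7.6.5: "exposure-adjusted SPM incidence rates (including multiple occurrences of unique events) will be presented by treatment group". Exposure itself is reported in 7.4.1.1: "Duration of each of the study treatments will be summarized by treatment group". Protocol 8.4.3 likewise plans only worst-grade-per-subject tables, for any occurrence and for Grade 3 or higher.

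**The concern.** Both arms are treated until progression or unacceptable toxicity (SAP 2.1), and the AE window closes 60 days after the last dose. Time at risk therefore follows time on treatment. The design assumes median PFS of 25 months on Ld and 33.75 months on E-Ld (SAP 5). If that holds and other reasons for stopping are similar, E-Ld subjects are watched longer, and a larger percentage will have had at least one serious or severe event even when the drug adds no risk per unit of time.

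The SAP accepts this reasoning for all AEs and for second primary malignancies, but does not extend it to the events that weigh most in a benefit-risk judgement. The all-grade SOC rate is a poor stand-in. If 15% of infection events are Grade 3 or higher (assumed; range 10 to 30%), a 30% rise in those events moves the SOC rate by only 0.15 × 0.30 = 4.5% (3 to 9%).

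**Working it through.** **1. The plan's own figures.** With exponential PFS, HR = 25/33.75 = 0.741, 482 events and one O'Brien-Fleming look at 70%, power is 90.5%. The nominal levels are 0.0148 (interim) and 0.0455 (final), as stated. Accrual of 24 per month gives about 332 events at month 41 and 484 at month 60, close to the planned 338 and 482. The design inputs can therefore be used to project exposure.

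**2. Inputs.** From the documents: medians 25 and 33.75 months, 375 subjects per arm, entry over 750/24 = 31.25 months, looks at months 41 and 60, and a 60-day tail (τ = 60/30.4375 = 1.97 months). Assumed, because the documents give neither: a constant event rate λ equal in both arms (10, 20 or 40 per 100 person-years), and dropout without progression at hazard d = 0 to 0.02 per month.

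**3. Formula.** Time on treatment has hazard μ = ln 2/median + d. For a subject with C months from entry to cut-off, time at risk is Y = min(T + τ, C), and

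P(at least one event) = 1 − e^(−λτ) + λ e^(−λτ) [1 − e^(−(λ+μ)(C−τ))] / (λ+μ),

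averaged over uniform entry. SE = √(p₁q₁/375 + p₂q₂/375).

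**4. Equal rates, equal dropout.** Mean treatment time without dropout is 17.7 vs 19.3 months at month 41 and 25.2 vs 28.8 at month 60. With 2% monthly dropout it is 18.2 vs 20.3 at month 60.

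| Rate per 100 PY | Month 41, d = 0 | Month 41, d = 2% | Month 60, d = 0 | Month 60, d = 2% |
|---|---|---|---|---|
| 10 | +1.0 | +0.7 | 19.2% vs 21.4%: +2.2 | +1.4 |
| 20 | +1.7 | +1.3 | 33.6% vs 37.1%: +3.5 | +2.2 |
| 40 | +2.6 | +1.9 | 53.0% vs 57.7%: +4.7 | +3.1 |

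The largest excess is 4.65/3.63 = 1.3 standard errors (month 60, no dropout). At month 41 the most is 2.58/3.63 = 0.7.

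**5. Where the excess shrinks or reverses.**

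- *Rare events* (2 to 5 per 100 person-years): +0.2 to +0.8 points with 2% dropout over both looks. Without dropout, +0.2 to +0.6 at month 41 and +0.5 to +1.3 at month 60.
- *Early events* (20 per 100 person-years in months 0-6, none after): 9.2% vs 9.3%.
- *Faster stopping of all drug on E-Ld* (2% vs 1% per month): mean treatment at month 60 is 21.2 vs 20.3 months, Ld first. The difference is −0.6, −1.0 and −1.3 points at 10, 20 and 40 per 100 person-years (−1.4 at 40 if the 60-day tail is not cut at the data cut-off).

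**6. The remedy's own bias.** In the early-event case, the 7.6.1 denominator (treatment plus 60 days) gives 4.26 per 100 person-years on Ld and 3.80 on E-Ld. The ratio 3.80/4.26 = 0.89 is an apparent 11% reduction under equal risk.

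**The case against.** The strongest reply is that little is lost. The tables are descriptive, and the percentage ever affected is a legitimate measure of risk under treatment to progression. Exposure is not ignored: duration is summarised by arm, and because each rate is shown with its event count, an arm's person-years follow as 100 × count / rate. By-subject SAE listings (7.6.2) supply SAE counts including repeats, and 7.6.1 plans a listing of all AEs. All of this stands. A reader could compute an SAE rate afterwards. This is less certain for Grade 3-4 AEs, because the listing columns are not specified. A later hand calculation is also not a prespecified arm comparison.

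The absence is also only as firm as the visible text. SAP 8.6 refers to a sponsor safety-data convention and 8.7 to a separate Data Presentation Plan, and neither was available. If either already specifies these tables, a cross-reference closes the point.

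Two wider readings are tempting but unsupported:

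- A reader might infer that grouped opportunistic infections are shown only as crude frequencies. They are defined in 7.6.4 as a set of preferred terms. Each term already gets a rate under 7.6.1, and all share one denominator, so the group rate is the sum of the planned rates. Only a subtotal is missing.
- A reader might add AEs leading to discontinuation to the gap. They do not belong there. Single drugs can be stopped (Protocol 4.3.3, SAP 7.4.4), and E-Ld has three drugs to stop against two. Person-years do not correct that.

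**Conclusion.** The point holds as a minor gap with a cheap remedy. In the visible SAP, Grade 3-4 AEs, SAEs and drug-related SAEs are compared by arm only as per-subject frequencies, which cannot separate event rate from time on treatment. Under equal constant rates of 10 to 40 per 100 person-years and equal dropout of 0 to 2% per month, the artefact is +0.7 to +2.6 points at month 41 and +1.4 to +4.7 at month 60.

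A reader might infer that the crude tables will overstate E-Ld toxicity by several points. The documents do not support that. They give no event rates or dropout, the top of the range needs zero dropout for 60 months, and early events or faster stopping on E-Ld remove or reverse the excess. What stands is that the crude table alone cannot show which case applies. No efficacy conclusion, error rate or stopping rule is touched.

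**What to change.** Add to SAP 7.6.2:

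> Beside the crude percentages, event counts and the exposure-adjusted incidence rate per 100 person-years (formula and denominator of 7.6.1) will be given by arm for SAEs, drug-related SAEs and Grade 3-4 AEs. Cumulative incidence of the first SAE and of the first Grade 3-4 AE, with death as a competing event, will be shown by arm.

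In 7.6.4, add the same rate for Grade 3-5 infections and, for opportunistic infections, a subtotal of the preferred-term rates already planned. Keep the 7.6.1 denominator so that all rates stay comparable. The curves are needed because the person-year rate assumes a roughly constant hazard.

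The cost is a few sentences, a few tables and one set of curves, from data already collected. Two limits should be stated with the output. Censoring at the end of the AE window may be informative. Precision is also modest: at 20 per 100 person-years, month 60 and no dropout, about 166 vs 187 events are expected, so the SE of the log rate ratio is at least √(1/166 + 1/187) = 0.11.

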6.1.1 Serious Adverse Event Collection and Reporting

Sections 5.6.1 and 5.6.2 in the Investigator Brochure (IB) represent the Reference Safety Information to determine expectedness of serious adverse events for expedited reporting. Following the subject's written consent to participate in the study, all SAEs, whether related or not related to study drug, must be collected, including those thought to be associated with protocol-specified procedures. All SAEs must be collected that occur during the screening period and within 60 days of discontinuation of dosing or within 30 days of the last visit for screen failures.

The investigator must report any SAE that occurs after these time periods and that is believed to be related to study drug or protocol-specified procedure.

An SAE report must be completed for any event where doubt exists regarding its seriousness.

If the investigator believes that an SAE is not related to study drug, but is potentially related to the conditions of the study (such as withdrawal of previous therapy or a complication of a study procedure), the relationship must be specified in the narrative section of the SAE Report Form.

SAEs, whether related or not related to study drug, and pregnancies must be reported to BMS (or designee) within 24 hours of awareness of the event. SAEs must be recorded on the SAE Report Form; pregnancies on a Pregnancy Surveillance Form (electronic or paper forms). The preferred method for SAE data reporting collection is through the eCRF. The paper SAE/pregnancy surveillance forms are only intended as a back-up option when the eCRF system is not functioning. In this case, the paper forms are to be transmitted via email or confirmed facsimile (fax) transmission to:

SAE Email Address: Refer to Contact Information list.

SAE Facsimile Number: Refer to Contact Information list.

For studies capturing SAEs through electronic data capture (EDC), electronic submission is the required method for reporting. In the event the electronic system is unavailable for transmission,

paper forms must be used and submitted immediately. When paper forms are used, the original paper forms are to remain on site.

SAE Telephone Contact (required for SAE and pregnancy reporting): Refer to Contact Information list.

If only limited information is initially available, follow-up reports are required. (Note: Follow-up SAE reports must include the same investigator term(s) initially reported.)

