where DUR is defined as (min (date of death, date of first dose in last cycle in timepoint + 28) - date of first dose in timepoint) / 7.

Dose intensity and relative dose intensity of elotuzumab will be summarized for the E-Ld group only.

Lenalidomide:

A subject's cumulative dose of lenalidomide is defined as the sum of each dose taken, as recorded in their medication diary.

Dose intensity and relative dose intensity for lenalidomide (mg/week) will be calculated separately for subjects who began the study at the standard daily dose, 25mg/day and those who, because of moderate renal impairment, began the study at < 25mg/day (at 10mg/day dose will be assumed when computing the RDI as this is the recommended dose for subject with moderate renal disease per protocol).

The lenalidomide dose intensity, per subject, will be calculated as:

$$7 \times \left(\frac{\text{cumulative dose of lenalidomide}}{(\text{min}(\text{date of 1st dose of lenalidomide in last cycle in which lenalidomide was administered}) + 28, \text{death date}) - \text{date of first dose of lenalidomide}} \right)$$

The relative dose intensity of lenalidomide is the dose intensity per week divided by the planned dose intensity per week, 131.25mg (or 52.5mg for subjects who begin therapy at < 25mg (10mg/day per protocol)).

Dexamethasone:

The dose intensity (mg/week) of dexamethasone, per subject, will be calculated separately for the period encompassing Cycles 1 and 2, Cycle 3-18 and Cycle 19 and beyond since dexamethasone dosing is different in these 3 periods.

Cycle 1 and 2:

$$7 \times \left(\frac{\text{cumulative dose of dexamethasone during the first two cycles}}{(\text{min}(\text{date of first dose of dexamethasone in last cycle among first 2 cycles} + 28, \text{death date}) - \text{date of first dose of dexamethasone in first cycle})} \right)$$

Cycle 3-18:

$$7 \times \left(\frac{\text{cumulative dose of dexamethasone during Cycle 3 - Cycle 18}}{(\text{min}(\text{date of first dose of dexamethasone in last cycle among 18 cycles} + 28, \text{death date}) - \text{date of first dose of dexamethasone in Cycle 3})} \right)$$

Cycle 19 and beyond:

$$7 \times \left(\frac{\text{cumulative dose of dexamethasone starting from Cycle 19}}{\left(\min(\text{date of first dose of dexamethasone in last cycle} + 28, \text{death date}) - \right) \text{date of first dose of dexamethasone in Cycle 19}} \right)$$

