7.6.6 Deaths

The number and percentage of deaths and the investigator-reported cause of death will be presented, by treatment group and overall. This will be summarized for all deaths, and for those reported on study treatment or within 60 days of discontinuing study treatment.

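### The exposure-adjusted AE rate adds 60 days after the last dose for every subject, with no cap at death or data cut-off, so absolute rates come out modestly low

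*SAP*

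**What the plan says.** SAP 7.6.1 plans exposure-adjusted AE rates per 100 person-years by system organ class and preferred term, in addition to the main frequency tables. It introduces the formula with the words "Exposure-adjusted incidence rate per 100 person-years will be used and will be calculated as". Each subject's time in the denominator is last dose date minus first dose date, plus 60, plus 1, converted to years. I read this as summed over the subjects in an arm. No minimum with another date appears.

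The numerator window has the same length. On-study AEs are those "with an onset date on or after the first dose until 60 days after the last dose". The protocol's collection rule for serious events agrees (section 6.1.1): "All SAEs must be collected that occur during the screening period and within 60 days of discontinuation of dosing".

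Elsewhere the SAP does bound time:

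- Dose intensity (SAP 7.4.1.3) takes a minimum with the death date, for example "where DUR is defined as (min (date of death, date of first dose in last cycle in timepoint + 28" days.
- The second-malignancy rate (SAP 7.6.5) stops at "subject death date or last known alive date".

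Deaths soon after the last dose are expected. SAP 7.6.6 tabulates "those reported on study treatment or within 60 days of discontinuing study treatment" separately.

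**The concern.** An exposure-adjusted rate is meant to divide events by the time in which they could have been observed. The printed denominator meets that aim for a subject who stopped treatment and was followed for the full 60 days. It does not for two groups:

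- Subjects whose last dose is less than 60 days before data cut-off. Most of these are still on treatment, because both arms are treated until progression or toxicity. Part or all of the added 60 days lies after the data end.
- Subjects who die within 60 days of the last dose. Part of the added time lies after death.

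In both groups the extra days enlarge the denominator and can add nothing to the numerator. The error runs in one direction only, and it scales every term in an arm by the same factor. At stake is the accuracy of the absolute rates reported per 100 person-years.

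**Working it through.** The documents state no AE rate or total person-time, so there is no figure of the plan's own to reproduce. The check compares two denominators, with F = first dose and L = last dose:

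- printed: L − F + 61
- capped: min(L + 60, death, cut-off) − F + 1

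**One subject.** Let s = L − F + 1. If the subject is dosed on the cut-off date, or dies on the day of the last dose, the printed time is s + 60 and the observable time is s. The rate is understated by 60/(s + 60): 66.7% for s = 30 days, 25.0% for 180, 14.1% for 365 and 7.6% for 730. For a subject off treatment and followed for 60 days it is 0%.

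**A whole arm: inputs.** From SAP section 5: 750 subjects at 24 per month (750/24 = 31.25 months of accrual), median PFS 25 and 33.75 months, and final PFS analysis at month 60. From protocol 8.5: interim at about month 41. Assumed, because the documents do not give them: exponential time on treatment, with median equal to the planning PFS median or shorter (12 and 15 months); 0 to 20% of those who stop dying within 60 days; and a last recorded dose 0 or 28 days before cut-off for subjects still on treatment.

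**Closed form, month 41, no gap, no early deaths.** Follow-up is uniform from 41 − 31.25 = 9.75 to 41 months. With λ = ln 2/median, the share still on treatment is P = (e^(−9.75λ) − e^(−41λ))/(31.25λ), and mean time on treatment is (1 − P)/λ. One month is 30.4375 days.

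- Control: λ = 0.0277, P = 0.510, mean 17.66 months = 537.4 days. Printed: 537.4 + 61 = 598.4 days. Unobservable: 60 × 0.510 = 30.6, plus about 0.9 for those who stopped within 60 days of cut-off (approximately λP × 1800/30.4375), giving 31.5. Capped: 566.9. Overstatement: 598.4/566.9 − 1 = 5.6%.
- Experimental: λ = 0.0205, P = 0.604, mean 586.8 days. Printed: 647.8. Unobservable: 36.2 + 0.7 = 37.0. Capped: 610.8. Overstatement: 6.1%.
- Effect on the between-arm rate ratio: (610.8/647.8)/(566.9/598.4) = 0.995.

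With a 28-day gap, the control figures become 537.4 − 28 × 0.510 + 61 = 584.1 printed against 566.9 capped, which is 3.0%.

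**Month 60, same method.** Control: P = 0.301, printed 827.9 against capped 809.3 days, 2.3%. Experimental: P = 0.409, printed 937.0 against capped 912.0, 2.7%.

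**Simulation over the assumed ranges** (person-time overstated; the last column is the factor by which the experimental-to-control rate ratio changes):

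| Cut-off | Time on treatment (medians, months) | Control | Experimental | Ratio factor |
|---|---|---|---|---|
| Month 41 | 25 / 33.75 | 3.0–6.1% | 3.3–6.5% | 0.9952–0.9987 |
| Month 41 | 12 / 15 | 2.2–4.9% | 2.5–5.3% | 0.9943–0.9990 |
| Month 60 | 25 / 33.75 | 1.3–2.8% | 1.5–3.1% | 0.9957–0.9990 |
| Month 60 | 12 / 15 | 0.6–2.1% | 0.8–2.3% | 0.9961–0.9999 |

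Expressed as understatement of the rate, the full range is 0.6 to 6.1%. The sign is the same in every scenario.

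**The case against.** The best defence is that the 60 days are deliberate. They match the AE and serious-AE windows, so numerator and denominator are aligned for every subject who completes the window. That stands, and it makes this an omission at the edges, not a wrong formula throughout. Several further points also stand:

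- For subjects still on treatment, time between the last recorded dose and cut-off is legitimate exposure, because events in it are recorded. The 28-day gap scenarios allow for this and roughly halve the effect when there are no early deaths.
- The second-malignancy rate is not a like-for-like comparison. Those events are collected throughout survival follow-up, so its time must run to death or last contact. The death cap in dose intensity is the fairer comparison.
- The tables are supplementary and untested, event counts appear beside the rates, and the topline list in SAP 8.7 names no exposure-adjusted AE table.
- Under SAP 2.3 the sponsor is told to unblind PFS at the interim only if the boundary is met. Otherwise the month-60 figures are the ones that matter for reporting.

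SAP 8.6 refers to external safety conventions, which might impose a cap. As described there, they cover AE analysis and incomplete dates. Nothing in either document says they limit exposure time, and 7.6.1 prints an explicit formula.

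A reader might infer that the formula flatters the experimental arm, since more of its subjects would still be on treatment if elotuzumab works. The figures do not support that as a concern. The two arms are inflated almost equally, and the rate ratio moves by at most about 0.6% in the table above.

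**Conclusion.** As written, the denominator includes time in which no AE could be recorded, and the absolute exposure-adjusted AE rates are modestly understated. If treatment runs to progression at the planning medians, person-time is overstated by roughly 3 to 6.5% at month 41 and 1 to 3% at month 60; shorter treatment lowers both ranges. These sizes rest on assumed treatment durations, early deaths and gaps before cut-off. The direction does not.

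The error does not extend to all deaths, only to those within 60 days of the last dose. It does not touch the frequency tables or any tested endpoint, and no claim that the formula favours either arm is made. Severity: minor.

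**What to change.** In SAP 7.6.1, define the denominator for each arm as the sum over treated subjects of

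[min(last dose date + 60 days, death date, last known alive date if lost to follow-up or consent withdrawn, data cut-off date) − first dose date + 1]/365.25,

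and state that the earliest of the applicable dates governs. Subjects observed for the full 60 days keep the time they have now.

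The cost is one line of SAP text and the matching programming, using dates already needed for other analyses. Reported rates will be slightly higher. No endpoint, test or trial procedure changes.
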